#### d) Follow-up data at 2 years visit

There is an established visit window defined in this study, the following postoperative follow-up data will be collected at 24 M (2 years)

It is assumed that the visits will be planned per standard of care. (Window set at +/- 2 month).

The following data will be collected in the eCRF:

- Date of visit (DD/MM/YYYY)

SYMBIOS		 symbios  Clinical Investigation Plan	F029.03
Date	27.11.2019		Distribution Informatique pdf
Auteur	BGA		
Contrôle	EBO		
Libération	RAQ		

- Name of Surgeon
- Physical examination
  - Weight, (between 20 and 250Kg)
  - Height, (between 80 and 250cm)
  - BMI (kg/m^2)
- Radiological examination per standard of care (ap, lateral, sunrise)- -
- Femoral patellar arthrosis, (applicable if it is an anatomic patella not a prosthetic implant), patellar tilt angle, patellar displacement, tibial slope, femoral component flexion, anatomical axis ( $\alpha$  and  $\beta$  angles), mechanical axis (HKA angle, F angle, T, angle, HKS angle)
- Surgeon reported scores will be collected during this visit:
  - KSRESS
  - Single Leg Stance Test or (SLS)
  - Timed up and go (TUG)
  
- Evaluate the radiolucent lines and radiographic loosening (according to the “Modern Knee Society Radiographic Evaluation System and Methodology for Total Knee Arthroplasty” version 2015) - Radiolucent lines; Femur frontal, Tibia frontal, Tibia profil, Patella
  
- Satisfaction of the patient based on performance evaluation of the evaluated device ORIGIN vs VANGUARD based on scoring via FJS questionnaire:
  - FJS score
  - A self-administrated patient satisfaction questionnaire.

The hypothesis regarding the scoring is that patients receiving ORIGIN implants will experience a more natural feel of the prosthesis during the first year after the surgery compared to patients receiving VANGUARD implants (as measured with FJS)

The overall patient satisfaction is expected to be improved after 2 years follow-up for ORIGIN vs VANGUARD.

FJS score at the postoperative visits will be collected per standard of care at the investigational site.

- Evaluate performance of the ORIGIN System vs VANGUARD PS at 2 years follow-up: clinical examination, and scoring. To evaluate/compare the clinical, functional and quality of life outcomes with the following scores:
  - The Knee Injury and Osteoarthritis Outcome Score (KOOS)
  - The Oxford Knee Score (OKS)
  - The EQ-5D-5L Score
  
- Safety evaluation of the implanted device ORIGIN:
  - Evaluation of Complications using the adverse event form (Cf. Adverse events form in XXI: APPENDICES)
  - Evaluation of Revisions for both Arms (It is also required to complete an AE form in case of revisions)
  - Global revision rate not higher (Interval 95%:  $p > 0.05$ ) than the state of the art.

SYMBIOS		 symbios  Clinical Investigation Plan	F029.03
Date	27.11.2019		Distribution Informatique pdf
Auteur	BGA		
Contrôle	EBO		
Libération	RAQ		

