	
 
• Severe collateral ligaments deficiency (requiring a more constrained prosthesis)
 
• Major anatomical deformities
 
• Severe flexion contracture or severe recurvatum
 
• Revision of a partial or total knee prosthesis
 
• Non-extractible material (e.g. screws, plate, intramedullary nail, osteosynthesis material...) which can create a conflict with any component of the prosthesis
 
• Distal and/or posterior and/or anterior femoral bone loss which exceeds the femoral component thickness
 
• Proximal tibial bone loss which exceeds the tibial component thickness (tibial tray + tibial insert)
 
• Allergy of any implant material
 

Collected data:	
 
• Baseline data: Year of birth, gender, weight, height, BMI, indication, medical knee history (number of surgeries, description, patient outcome), radiological examination or CT scan
 
• Surgery procedure: side of implantation, implanted devices ORIGIN (instruments included) vs VANGUARD PS, surgery total duration time, perioperative complications and difficulties, Surgeon satisfaction regarding devices and instruments, Femoral and tibial sizing, patellar resurfacing.
 
• Postoperative Follow-up: (1y, 2y) follow-up visits: Physical examination, weight, height, BMI Rx examination, safety evaluation, scoring via a questionnaire: FJS score (at 1y and 2y FU visits), patient satisfaction, surgeon reported scores (Knee Society Radiographic Evaluation and Scoring System (KSRESS, the Knee Society Score (KSS) (Objective Knee Indicators only), the Single Leg Stance Test (SLS) , the Timed Up & Go test (TUG) )and patient reported scores: KOOS, OKS, FJS; EQ-5D-5L, a self-administrated patient satisfaction questionnaire and complications, revisions.
 
 
FJS and other reported scores (at the postoperative visits) will be collected per standard of care at the investigational site and will be compared at each follow-up among ARM 1 and 2.

Clinical Affairs Manager:	[name]
Clinical Monitor:	TRIUM (Clinical Monitor)
eCRF platform:	Bepatient

SYMBIOS		 symbios  Clinical Investigation Plan	F029.03
Date	27.11.2019		Distribution Informatique pdf
Auteur	BGA		
Contrôle	EBO		
Libération	RAQ		

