### B. Clinical endpoints

#### a) *Primary endpoints*

- The hypothesis regarding the scoring is that patients receiving ORIGIN implants will experience a more natural feel of the prosthesis during the first year after the surgery compared to patients receiving VANGUARD implants (as measured with FJS)
- The primary endpoint of this study is:

SYMBIOS		 symbios  Clinical Investigation Plan	F029.03
Date	27.11.2019		Distribution Informatique pdf
Auteur	BGA		
Contrôle	EBO		
Libération	RAQ		

- To compare the ability of patients to forget their operated knee at 1 year after the surgery, measured by the Forgotten Joint Score 12 (FJS-12 Knee).
- To compare patient satisfaction regarding the surgery with a CE marked custom-made implant (ORIGIN®) versus off-the-shelf (VANGUARD PS) device. A short self-reported questionnaire will be used.

*b) Secondary endpoints will evaluate clinical performance and safety of ORIGIN System:*

- **Secondary endpoints:**

- Evaluate the success of the procedure
- Evaluate surgeon satisfaction regarding the use of implants and instruments
- Evaluate outcomes: complications & revision rate with the ORIGIN SYSTEM at the last (2y) follow-up visit
- To compare the PROMs between the two groups at 1y follow-up and 2y follow-up visits.
- Evaluate performance of the ORIGIN System vs VANGUARD PS at 2 years follow-up: clinical examination and scoring.
- To evaluate/compare the clinical, functional and quality of life outcomes using the following four scores:
  - Clinical examination
  - The Knee Injury and Osteoarthritis Outcome Score (KOOS)
  - The Oxford Knee Score (OKS)
  - The EQ-5D-5L Score
  - A self-administrated patient satisfaction questionnaire.
- To evaluate/compare the clinical, functional and quality of life outcomes with the following surgeon reported scores:
  - The Knee Society Score (KSS) (Objective Knee Indicators only)
  - Knee Society Radiographic Evaluation and Scoring System (KSRESS)
  - The Single Leg Stance Test (SLS)
  - The Timed Up & Go test (TUG)
- Radiological evaluation:
  - X-rays: AP, lateral, sunrise, long leg weight bearing film
  - Femoral patellar arthrosis: Iwano classification (stage 1 mild to 4 very severe),
  - KRESS Radiological assessment: Patellar tilt angle, patellar displacement, tibial slope, anatomical axis (angles  $\alpha - \beta$ ), mechanical axis, (HKA angle, F angle, T angle, HKS angle)

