  - Evaluate the radiographic limb alignment, radiolucent lines and radiographic loosening (according to the “Modern Knee Society Radiographic Evaluation System and Methodology for Total Knee Arthroplasty” version 2015)

 The self-administered patient satisfaction scale for primary hip and knee arthroplasty. N. Mahomed, Rajiv Gandhi, Lawrence Daltroy, and J. N. Katz  
doi:10.1155/2011/591253

SYMBIOS		 symbios  Clinical Investigation Plan	F029.03
Date	27.11.2019		Distribution Informatique pdf
Auteur	BGA		
Contrôle	EBO		
Libération	RAQ		

Endpoints evaluation is based on a significant improvement between preoperative & last follow-up at two years.

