## F. Description of all clinical investigation related subject procedures

### a) Preoperative data

There are established visit windows defined in this study based on standard clinical practice (Cf. XXI.APPENDICES. B. SCHEDULE OF ASSESSMENT).

During the preoperative visit, the following baseline data will be collected:

- o Subject Information or consent (at least 24h prior to the preoperative visit) – Date of consent

SYMBIOS		 symbios  Clinical Investigation Plan	F029.03
Date	27.11.2019		Distribution Informatique pdf
Auteur	BGA		
Contrôle	EBO		
Libération	RAQ		

- If consent obtained, date of preoperative visit (DD/MM/YYYY)
- Date of randomization and Arm attribution Group 1 (ORIGIN) or 2 (VANGUARD)
- Inclusion/exclusion criteria
- Demographic data:
  - Gender: Male, female
  - Year of birth, (DD/MM/YYYY)
  - Age of patient: (YY)
  - Weight, (between 20 and 250Kg)
  - Height, (between 80 and 250cm)
  - BMI (kg/m^2)
- Indication : Severe painful and/or disabled knee joint, resulting from:
  - Non-inflammatory degenerative knee joint disease
  - Osteoarthritis, necrosis, post traumatic arthritis

Or Inflammatory knee joint disease:  
Rheumatoid arthritis
- Medical Knee history
  - number of previous knee surgeries
  - description of knee surgeries: medial meniscectomy, lateral meniscectomy, arthroscopy, tibial/femoral osteotomy, other to specify
- Radiological examination
  - If patient is assigned to Arm 1: Pre-op CT Scan will be performed for the design of the ORIGIN prosthesis. Pre-op RX will be performed as well per standard of care
  - If patient is assigned to Arm 2: Pre-op RX will be performed for the implementation of the VANGUARD PS system. (AP, lateral, sunrise)
- Surgeon reported scores:
  - KSS score (Objective Knee Indicators only)
  - X-rays: AP, lateral, sunrise, long leg weight bearing film
  - Femoral patellar arthrosis (Iwano classification (stage 1 mild to 4 very severe)),
  - Knee Society Radiographic Evaluation and Scoring System (KSRESS): patellar tilt angle, patellar displacement, tibial slope, anatomical axis (angles  $\alpha - \beta$ ), mechanical axis (HKA angle, F angle, T angle, HKS angle)
  - Single Leg Stance test (SLS)
  - Timed up and go (TUG)
- Patient reported scores:
  - KOOS Score
  - OKS Score
  - FJS Score
  - EQ-5D-5L Score
  - A self-administrated patient satisfaction questionnaire.

---

 Long leg, knee in 2 planes and patella sunrise

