### c) Follow-up data at 1-year visit

There is an established visit window defined in this study, the following postoperative follow-up data will be collected at 12M (1 year).

The follow-up window is flexible and is set as a guidance to +/-1M for the first visit at 1 year.

The following data will be collected in the eCRF:

- Date of visit (DD/MM/YYYY)
- Name of Surgeon
- Physical examination
  - Weight, (between 20 and 250Kg)
  - Height, (between 80 and 250cm)
  - BMI (kg/m^2)
- Radiological examination per standard of care (ap, lateral, sunrise)-
- Femoral patellar arthrosis (applicable if it is an anatomic patella not a prosthetic implant), patellar tilt angle, patellar displacement, tibial slope, femoral component flexion, anatomical axis ( $\alpha$  angle,  $\beta$  angle), mechanical axis (HKA angle, F angle, T angle, HKS angle)

SYMBIOS		 symbios  Clinical Investigation Plan	F029.03
Date	27.11.2019		Distribution Informatique pdf
Auteur	BGA		
Contrôle	EBO		
Libération	RAQ		

- Surgeon reported scores will be collected during this visit:
  - The Knee Society Score (KSS) (Objective Knee Indicators only)
  - Knee Society Radiographic Evaluation and Scoring System (KSRESS)
  - Single Leg Stance Test or (SLS)
  - Timed up and go (TUG)
- Evaluate radiographic loosening (according to the “Modern Knee Society Radiographic Evaluation System and Methodology for Total Knee Arthroplasty” version 2015)
- Radiolucent lines; Femur, frontal Tibia frontal, Tibia profil, Patella
- Satisfaction of the patient based on performance evaluation of the evaluated device ORIGIN vs VANGUARD based on scoring via FJS questionnaire:
  - FJS score
  - A self-administrated patient satisfaction questionnaire. (3 questions)

The hypothesis regarding the scoring is that patients receiving ORIGIN implants will experience a more natural feel of the prosthesis during the first year after the surgery compared to patients receiving VANGUARD implants (as measured with FJS).

The overall patient satisfaction is expected to be improved after 1-year follow-up for ORIGIN vs VANGUARD.

FJS score at the postoperative visits will be collected per standard of care at the investigational site.

- Evaluate performance of the ORIGIN System vs VANGUARD PS at 1-year follow-up: clinical examination, and scoring. To evaluate/compare the clinical, functional and quality of life outcomes with the following scores:

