## B. SCHEDULE OF ASSESSMENT

Patient visits/Activities	1 Preop erative	2 OP	3 12 Months  (1 Year)	4 24 Months (2 Years) 
Patient Informed Consent	X			
Demographic data	X			
Indications	X			
Medical History	X			
Clinical examination	X		X	X
Randomization: allocation to two study arms: CT-Scan (KNEE PLAN) - ARM 1: ORIGIN Group	X			
Preoperative Radiological assessment for ARM 1& ARM 2	X			
Surgery		X		
Clinical Examination at 1 y and 2 y follow-up			X	X
Radiological Assessment at 1y and 2 y FU			X	X
Knee Injury and Osteoarthritis Outcome Score (KOOS)	X		X	X
Oxford Knee Score (OKS)	X		X	X
Quality of life (EQ-5D-5L)	X		X	X
Forgotten Joint Score (FJS)	X		X	X
Patient satisfaction questionnaire	X		X	X
Complications & Revisions		X	X	X

[figure not shown]
 The follow-up window is flexible and is set as a guidance to +/-1M for the first visit.

 For FU visits at 2 years, it is assumed that the visits will be planned per standard of care. (window set at +/- 2 month)

SYMBIOS		 Clinical Investigation Plan	F029.03
Date	27.11.2019		Distribution Informatique pdf
Auteur	BGA		
Contrôle	EBO		
Libération	RAQ		

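### The plan contradicts itself on whether the Knee Society Score is collected at 2 years: the synopsis includes it, the 2-year visit list omits it, and the schedule does not settle the matter

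*Combined protocol and SAP*

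**What the plan says.** **Endpoint.** Section VI.B introduces four secondary measures with "To evaluate/compare the clinical, functional and quality of life outcomes with the following surgeon reported scores". They are KSS, KSRESS, SLS and TUG. No visit is attached to that bullet. A separate bullet reads "Evaluate performance of the ORIGIN System vs VANGUARD PS at 2 years follow-up: clinical examination and scoring", and the section closes with "Endpoints evaluation is based on a significant improvement between preoperative & last follow-up at two years".

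**Synopsis.** The postoperative entry under collected data covers the 1-year and 2-year visits together. Its surgeon-reported scores include "the Knee Society Score (KSS) (Objective Knee Indicators only"), alongside KSRESS, SLS and TUG. It adds that the reported scores are to be compared between the arms at each follow-up.

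**Visit lists in VIII.F.** The preoperative list (VIII.F.a) has "KSS score (Objective Knee Indicators only"). The 1-year list (VIII.F.c) has "The Knee Society Score (KSS) (Objective Knee Indicators only"). The 2-year list (VIII.F.d) is headed, like the 1-year list, "Surgeon reported scores will be collected during this visit", but names only KSRESS, SLS and TUG.

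**Schedule (XXI.B).** Each patient-reported score has its own row. The surgeon-reported scores have none. The nearest entries are a radiological row and "Clinical Examination at 1 y and 2 y follow-up".

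**The concern.** Section VIII.F.d is the operative list: it states what is to be entered in the eCRF at 2 years. A coordinator or eCRF builder working from it would have no instruction to record KSS at the time point that VI.B uses for evaluating endpoints. The schedule, to which VII.A and VIII.F.a refer the reader, would not correct the mistake.

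The loss could not be made good later. The score is assessed by a clinician at the visit, and section X.e rules out imputation and drops subjects with missing data from the analysis concerned. If some staff followed the synopsis and others the visit list, 2-year KSS would be patchy instead of absent. In an unblinded trial, patchy collection of a clinician-assessed score is also open to bias.

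**Working it through.** This is mainly a comparison of texts. Setting the places side by side:

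| Place in the plan | KSS | KSRESS | SLS | TUG |
|---|---|---|---|---|
| VI.B, secondary endpoints | named | named | named | named |
| Synopsis, collected data, 1y and 2y | listed | listed | listed | listed |
| VIII.F.a, preoperative | listed | listed | listed | listed |
| VIII.F.c, 1 year | listed | listed | listed | listed |
| VIII.F.d, 2 years | **absent** | listed | listed | listed |
| XXI.B, schedule | no row | no own row | no row | no row |

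1. **Is there a conflict over 2-year KSS?** Yes. The synopsis requires it and VIII.F.d leaves it out. KSS is the only one of the four scores treated differently at 2 years, and no reason is given.

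2. **Does anything settle the conflict?** The available text gives no order of precedence between synopsis and body. The schedule has no KSS row at any visit, including those where the body plainly requires KSS, so its silence is not evidence either way. Reading the schedule's clinical examination row as containing KSS has no support: VI.B lists clinical examination and KSS as separate items, and VIII.F.c lists KSS separately from the physical examination. VIII.F.d keeps the physical examination but not KSS.

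3. **Is there a conflict over the other three scores?** No. VIII.F.d lists KSRESS, SLS and TUG at 2 years, in agreement with the synopsis. For these the schedule is merely less detailed than the body.

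4. **How many patients could be affected?** Planned enrolment is 140, or 70 per arm (VII.C, X.a). The plan allows a 10% loss by the end of the study (VII.A), taken as 7 per group (X.a).
   - Expected at 2 years: 140 × (1 − 0.10) = 126.
   - Per arm: 70 − 7 = 63.

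   So 126 is the whole expected 2-year cohort, and therefore the ceiling on missing 2-year KSS. It is not an estimate of how many would be missing.

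5. **Does this touch the sample size?** No. The plan's figure rests on the Forgotten Joint Score: n = (2 / 0.5²) × (1.96 + 0.84)² = 8 × 7.84 = 62.72, rounded up to 63 per group, and 63 + 7 = 70. This reproduces the plan, and KSS does not enter it.

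**The case against.** The strongest reply is that the plan does prescribe KSS at 2 years, because the synopsis says so, and that section XI.a promises an eCRF capturing everything the protocol requires. The case report forms are a separate document, so nobody reading the plan alone can say that the 2-year field is missing. This stands against the stronger reading that a reader might infer, namely that the 2-year KSS comparison is bound to have no data. The documents show a contradiction, not a certain loss. The reply does not remove the contradiction, however: VIII.F.d is itself a statement of what the eCRF requires at 2 years, so a form built to match it would honour that section and still lack KSS.

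A second reply is that the surgeon-reported scores carry no time point in VI.B, and that the synopsis endpoint entry ties the 2-year evaluation to the patient-reported scores. That is fair. The expectation of a 2-year KSS rests on the synopsis data list and on the general closing sentence of VI.B. Those two are enough to make the omission an inconsistency, but they leave open that it was intended.

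A reader might also infer from the schedule that SLS and TUG are at risk at 2 years. They are not, because VIII.F.d names both.

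**Conclusion.** The inconsistency is real and should be reconciled. It concerns one of the four surgeon-reported secondary scores at one visit.

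If VIII.F.d is followed literally, up to about 126 patients would have no 2-year KSS, and neither the change from the preoperative visit to 2 years nor the 2-year comparison between arms could be made for that score. If the synopsis is followed, nothing is lost. The documents do not show which will happen. The figure of 126 assumes full enrolment and exactly the planned 10% loss.

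KSS at baseline and 1 year remains specified, so a 1-year between-arm comparison is still possible. The primary endpoint and the sample size are untouched.

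**What to change.** - In VIII.F.d, add KSS to the surgeon-reported scores in the form already used preoperatively, "KSS score (Objective Knee Indicators only"), so that the list agrees with the synopsis.
- In XXI.B, add a KSS row marked at the preoperative, 12-month and 24-month visits.
- Confirm that the 2-year eCRF has the field.
- If leaving KSS out at 2 years was deliberate, correct the synopsis data list instead, and state in VI.B that KSS is evaluated to 1 year only.

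Schedule rows for KSRESS, SLS and TUG would be optional tidying, since VIII.F.d already collects them at 2 years.

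The cost is a few lines of text, an eCRF check and, because section XIII requires ethics committee approval of any protocol amendment, one submission, which can be combined with other changes. The documents give no time needed for the KSS assessment, but the synopsis already implies it at this visit. The change should be in force before the first 2-year window opens, at 24 − 2 = 22 months after the first surgery.

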### e) Scores

Cf. Forgotten Joint score (FJS) – Chapter XXI. APPENDICES. E. PATIENT SELF-QUESTIONNAIRE

The Forgotten Joint Score (FJS) is a joint-specific questionnaire developed in 2012 (Behrend et al. 2012) with the aim to measure PRO of joint disorders (Hamilton et al. 2017). FJS is designed to measure the ability of the patient to “forget” about their problematic joint after treatment. FJS is available in 3 versions: hip, knee, and shoulder. In the following editorial: *The Forgotten Joint Score Don't Compare Apples to Oranges,* “The Forgotten Joint Score asks the simple question, “Are you aware of the joint that had surgery?” Essentially, does the patient have any sense that there has been surgery on the limb or joint? Although it has been validated as a reliable testing technique in specific surgical procedures, it has not been validated as a method of comparing 2 dissimilar surgical procedures.” This is why this score will only be used to compare patient satisfaction while undergoing a surgery with ORIGIN or with VANGUARD systems.

FJS is defined in 12 questions:

- Functional outcome, pain, stability and daily living ...but additional
- Activity and Sport

The outcome Score is between 0-4. Zero is best outcome. Low score means high satisfaction. All responses are summed and multiplied by 25 (Total= 0-100)

Overall patient satisfaction will therefore be calculated based on patients PROMs. (Patient reported outcome measures) This score will be used to evaluate patient satisfaction with ORIGIN vs VANGUARD which should lead to a higher score (>13.4 points)

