### B. Evaluation of relevant clinical data (Registries, PMS, PMCFs)

As part of Symbios PMS, a prospective surveillance is established on the evaluated device. It includes the surveillance of all relevant scientific journals and regular electronic database (EMBASE, PubMed) review. A list of pertinent publications for this study is in the section XX. BIBLIOGRAPHY.

post-market surveillance also includes the current ongoing Symbios PMCF study CLIN-G-008: Evaluation of the performance and the safety of the ORIGIN® knee prosthesis and of the KNEE-PLAN® ORIGIN® instruments. (Study launched in 2018)

This study is related to 399 primary Total Knee Replacements, performed between 2018 and 2020. Indications are coherent with Instructions for Use. The mean follow-up is 1.0 year (max 1.6 year)

Preliminary results:

- Number of procedures                    399
- Gender                                        Females 52 % / Males 48 %
- Age     Mean 71.0 years
- Mean weight                                81.1 kg (33-177)
- Mean height                                168.7 cm (143-193)
- Mean Body Mass Index                28.4 (13-68)

Outcomes regarding performance:

- FJS score: compared to preoperative value, the Forgotten Joint Score is significantly improved at 3-6 months and at 1 year. According to the validated grading, the mean preoperative score (12.9/100) is poor and the mean score at 3-6 months (42/100) and at 1 year (60.5/100) is good
- Oxford Knee Score: compared to preoperative value, the Oxford Knee Score is significantly improved at 3-6 months and 1 year. According to the validated grading, the mean preoperative score (24.8/48) is poor and the mean score at 3-6 months (36.6/48) and at 1 year (41.2/48) is good
- ✓ Many of the patients are satisfied about their surgery (96% of satisfied or very satisfied)

At a mean follow-up of 1.0 year:

- ✓ The per-operative complication rate is 0.25%

[figure not shown]
SYMBIOS		 symbios  Clinical Investigation Plan	F029.03
Date	27.11.2019		Distribution Informatique pdf
Auteur	BGA		
Contrôle	EBO		
Libération	RAQ		

- ✓ The postoperative complication rate without revision is 3.25%
- ✓ The postoperative complication rate with revision is 0.25%

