#### *b) Patient Reported Outcomes Measures (PROMs)*

The Minimal Clinical Important Difference (MCID) is the minimum difference in Patient Reported Outcomes Measures (PROM) that is meaningful for the patient.

With a distribution-based approach, the ability of patient to discriminate each task after the surgery is approximately half a Standard Deviation. Therefore, for the purpose of this study, MCID will be evaluated by half of the Standard Deviation (SD) of the Forgotten Joint Score. (cf. Primary endpoints)

A literature review on the FJS in TKR has been performed (cf. Chapter XX: Bibliography). Literature shows that the SD of the FJS can be evaluated at 26.8 points.

For the purpose of this study, half of the SD is set at 13.4 points for patient satisfaction between Origin versus VANGUARD.

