### e) *Statistical Methods and Analysis*

All analyses will be described in a Statistical Analysis Plan (SAP) which will be completed prior to analysis. No interim analysis is planned.

Any deviations from this section and/or the Statistical Analysis Plan will be described and justified in the Final Clinical Study Report, as appropriate.

No statistical techniques will be used to impute missing data for continuous or categorical outcomes. If a subject's data are missing for any reason, that subject will not be included in that portion of the analysis. The number of subjects included in each analysis will be reported so that the reader can assess the potential impact of missing data.

Additional (annual) reports providing only descriptive statistics will only be written upon request of the EC/IRB and/or Regulatory Authority, as applicable.

For statistical analysis, patient satisfaction results will be analyzed into the knee awareness as:

- Never
- Almost never
- Seldom
- Sometimes
- Mostly

The subjects that required further procedures or surgeries on their knee in the initial six months were excluded from this analysis. These patients were excluded from analysis because the outcome and satisfaction scores were likely to be highly influenced by the early additional procedure, and the study was not powered to evaluate the revision rates associated with two implants.

Statistical differences could be identified in:

- Baseline demographics between ORIGIN vs VANGUARD in patient satisfaction, including slightly differences in age, comorbidities and sex.
- Surgeon overall satisfaction regarding both implants ORIGIN and VANGUARD and possible surgical factors who could play a role in the patient outcome or on the performance of the implant?
- Demonstrate superiority of ORIGIN over VANGUARD: higher score by 13.4 points based on MCID evaluation of PROMs.
- If a modular stem is used it could impact radiological analysis: radiolucencies for instance and tibial loosening

SYMBIOS		 symbios  Clinical Investigation Plan	F029.03
Date	27.11.2019		Distribution Informatique pdf
Auteur	BGA		
Contrôle	EBO		
Libération	RAQ		

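### The scoring rule for the primary endpoint (FJS-12) gives 0–1200 instead of 0–100 and makes a low total good, while the rest of the plan treats a higher score as better

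*Combined protocol and SAP*

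**What the plan says.** The primary endpoint (Section VI.B.a) is "To compare the ability of patients to forget their operated knee at 1 year after the surgery, measured by the Forgotten Joint Score 12". The score is specified in Section VIII.F.e (Scores): "FJS is defined in 12 questions", each response scored from 0 to 4, and then "Zero is best outcome. Low score means high satisfaction. All responses are summed and multiplied by 25 (Total= 0-100".

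Four other places state or imply a direction or a scale:

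- The closing paragraph of Section VIII.F.e expects a benefit with ORIGIN, "which should lead to a higher score (>13.4 points".
- Section VI.C (Hypothesis) expects a result 13.4 points higher with ORIGIN than with VANGUARD.
- Section X.e (Statistical Methods and Analysis) has "Demonstrate superiority of ORIGIN over VANGUARD: higher score by 13.4 points based on MCID evaluation of PROMs".
- Section IV.B, reporting the sponsor's ongoing PMCF study of the same device, states that "the mean preoperative score (12.9/100) is poor and the mean score at 3-6 months (42/100) and at 1 year (60.5/100) is good".

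The trial was sized on this score. Section X.b says "Literature shows that the SD of the FJS can be evaluated at 26.8 points" and takes half of that, 13.4, as the difference of interest.

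**The concern.** There are two separate faults in one rule.

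**Range.** The sum of 12 items scored 0–4, multiplied by 25, cannot have a range of 0–100.

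**Direction.** The rule makes zero the best result and a low score a good one, then goes straight from items to total with no reversal. Every other statement about the FJS in the plan needs a high total to be good.

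The direction fault is the more dangerous of the two. A total of several hundred would be noticed. A programmer who repairs only the range, by averaging, gets plausible values between 0 and 100 that run backwards. The sample-size formula is two-sided, and a two-sided test can reach significance in either direction. If the result is then read against the statement that superiority means a higher score, a worse outcome with ORIGIN would be labelled as superiority.

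The plan's safeguards may not catch this. Section XI.c calls for validation of the protocol-specific implementation of the data-capture system, so the protocol text is the natural reference for that check. Section VIII.F.e points to Appendix XXI.E for a patient questionnaire, but that appendix is a list of references, and its FJS entry gives only citations.

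**Working it through.** **Inputs.** Number of items 12, item range 0–4, multiplier 25, stated total 0–100 (Section VIII.F.e). Earlier FJS means 12.9, 42 and 60.5 out of 100 (Section IV.B). SD 26.8 and difference 13.4 (Section X.b). z-values 1.96 and 0.84, 63 per group, plus 7 for loss (Section X.a).

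**1. Range of the total**

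- As written: 12 × 4 = 48; 48 × 25 = 1200. The range is 0–1200, 12 times the stated maximum.
- With the mean item score: 4 × 25 = 100. This reproduces the stated 0–100.
- A literal total stays at or below 100 only if the item sum is at most 100/25 = 4, out of a possible 48.
- One step on one item is worth 25 points as written, more than the whole 13.4-point difference. On 0–100 it is worth 25/12 = 2.1 points.

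**2. Direction, using the sponsor's own means**

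Take the Section IV.B values as correctly scored, that is S = 100 − 25 × mean item score. Then mean item score = (100 − S)/25. The averaged but unreversed score is 25 × mean, and the literal total is 12 × 25 × mean.

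| Time point | Section IV.B | Mean item score | Averaged, not reversed | Literal rule |
|---|---|---|---|---|
| Preoperative | 12.9 | 3.484 | 87.1 | 1045 |
| 3–6 months | 42 | 2.32 | 58.0 | 696 |
| 1 year | 60.5 | 1.58 | 39.5 | 474 |

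The values in Section IV.B rise with improvement. Under the rule in Section VIII.F.e, with or without averaging, they fall.

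**3. Effect on the sample size**

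- The plan's figure: n = 2/ES² × (1.96 + 0.84)², with ES = 13.4/26.8 = 0.5, gives 2/0.25 × 7.84 = 62.72, so 63 per group; 63 + 7 = 70. Both stated figures are reproduced.
- If difference and SD are both multiplied by 12: 160.8/321.6 = 0.5, so n is again 63. Rescaling alone does not change power or p-values.

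**4. If 13.4 were held fixed against literal totals (hypothetical)**

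13.4/12 = 1.12 points on 0–100, and 1.12/26.8 = 0.042 SD. A clinically trivial difference would meet the benchmark.

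**The case against.** The strongest reply is that the sentences making low scores good come directly after the 0–4 item range and before the total is mentioned. They can be read as describing item coding only, in which case the rule omits a reversal rather than asserting the wrong direction. The intended scale is also plain: the rule itself says 0–100, Section IV.B reports scores out of 100 with higher as better, and Sections VI.C and X.e agree.

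An error would probably show itself too. Literal totals would nearly all exceed 100. Because the FJS is also collected before surgery, an unreversed score would fall from baseline to follow-up, against the sponsor's earlier experience. The SAP is still to be written and the CRFs are separate documents; either may hold a correct derivation. Finally, no text clearly defines a test against a fixed 13.4, which serves mainly as the design difference.

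Most of this is fair. A drafting error is the likely explanation, the inverted-result scenario is possible rather than probable, and the figures in step 4 apply only under that assumption. But the item-coding reading does not repair the rule: with no division and no reversal stated, the total inherits the direction of its items. A correct SAP would contradict the protocol, not cure it.

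**Conclusion.** The concern holds on both counts. The rule gives 0–1200 against a stated 0–100, a 12-fold discrepancy that follows from the document's own numbers without any assumption. The direction it implies is opposite to that used in Sections IV.B, VI.C and X.e and in the closing paragraph of Section VIII.F.e itself.

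The rescored means (87.1 and 39.5 averaged; 1045 and 474 literal) assume that the Section IV.B values were scored on a 0–100, higher-is-better scale, as their grading indicates. Design, power and sample size are unaffected. The harm is confined to the sign of the primary result and to the meaning of 13.4 points. Because this is the only scoring rule visible for the primary endpoint, it must be corrected before analysis. Whether the eCRF or the future SAP already scores the instrument correctly cannot be determined from these documents.

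**What to change.** Replace the rule in Section VIII.F.e with text such as: *Each item is coded 0 (best, never aware of the joint) to 4 (worst). FJS-12 = 100 − 25 × the mean of the item scores. The range is 0–100 and a higher total is better.* Remove the instruction to sum and the sentence equating a low score with high satisfaction. This formula is the one that satisfies the plan's own item range, multiplier, total range and direction of benefit. Use the same direction in Sections IV.B, VI.C, VIII.F.e and X.e, and repeat the formula in the SAP.

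Before database lock, check the eCRF derivation against the cited instrument and with three test cases: all items 0 gives 100, all items 2 gives 50, all items 4 gives 0.

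Two related points are best settled in the same edit, although the finding does not depend on them:

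- **Unanswered items.** Section X.e says "No statistical techniques will be used to impute missing data for continuous or categorical outcomes", but not whether one blank item makes the whole score missing. Under a plain sum, a blank adds nothing and so counts as the best answer. The SAP should state the rule.
- **Form of the endpoint.** State that the primary comparison uses the continuous 0–100 score, since the SD of 26.8 and the difference of 13.4 refer to that scale.

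The cost is a wording amendment to the protocol, matching SAP text and a short check of the score derivation. Design, visits and sample size do not change.
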